4 DATA SETS TO BE ANALYSED

The following analysis sets will be used for the statistical analysis and presentation of data during the DB (Double Blind) period:

Safety set (DB-SAF): All randomised subjects who received at least one dose of the trial drug, will be analysed according to actual treatment.

Full analysis set (DB-FAS): All randomised subjects, will be analysed according to randomised treatment.

Per-protocol set (DB-PPS): All randomised subjects who have completed Visit 8 and are deemed to have no important protocol deviations that could interfere with the objectives of this trial, will be analysed according to actual treatment.

Important deviations of eligibility criteria and other deviations from the protocol will be assessed by TFS in cooperation with the sponsor. Important deviations from the protocol may lead to exclusion of a subject from the DB-PPS. All such decisions will be made and documented before the trial database is unblinded.

If not otherwise stated, all efficacy endpoints will be analysed based on DB-FAS. Although analyses of primary and key efficacy endpoints will be performed on both the DB-FAS and the DB-PPS, the DB-FAS will be considered the primary analysis population.

Safety summaries will be performed on the safety set (DB-SAF).

Analysis sets to be applied for the follow-up period will correspond to the analysis sets for the double-blind period, although the follow-up period analysis sets will include only subjects not withdrawing from the trial before the follow-up period begins and who has at least one follow-up period data-point. The follow-up period FAS and SAF will be denoted FU-FAS and FU-SAF, respectively. In addition, the subgroup of subjects receiving the intermittent dosing regimen during the follow-up period (i.e. the vast majority of follow-up period subjects) will be evaluated alone (FU-MOL-INT).

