8.4 Withdrawal of Subjects from Therapy or Assessment

8.4.1 Withdrawal from the Trial

Subjects are free to discontinue their participation in the trial at any time. Withdrawal from the trial will not affect or prejudice the subject's further care or treatment. Potential reasons for withdrawal of subjects from the trial are:

- Screening failure
- The decision of a subject to withdraw from the trial (including if the subject withdraws informed consent)
- Subject is lost to Follow-up
- Other reason(s)

The reason and date the subject is withdrawn from the trial will be documented in the electronic case report form (eCRF) (e.g. lost to Follow-up, consent withdrawn, incorrect enrolment, AEs, etc.). If a subject is withdrawn from the trial, the investigator should attempt to complete all required trial assessments (such as those at Week 24 if withdrawn during the Double-blind treatment period).

All AEs should be followed-up according to *Section 11.2*.

If a subject is withdrawn from the trial, all data collected until the time of withdrawal will be used in the analyses.

Subjects who withdraw before randomisation will be considered screen failures.

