8.4.2 Discontinuation of Double-Blind Treatment

Subjects may be discontinued from double-blind treatment and assessments at any time, if deemed necessary by the investigator.

Potential reasons for discontinuation of double-blind treatment are:

- Lack of efficacy/worsening of disease
- Unacceptable AE

- Serious hypersensitivity reaction
- Pregnancy

Those who discontinue double-blind treatment will not automatically be withdrawn from the trial but will be encouraged to continue to follow the same visit schedule.

For example: if double-blind treatment is discontinued at Week 8 (Visit 4) the subject will be encouraged to attend the remaining visits in the Double-blind treatment period (Weeks 12, 16, 20 and 24) and continue into the Follow-up period. If the subject is reluctant to agree to 4-weekly visits, the investigator should request attendance at Week 24 (Visit 8) as a minimum.

The reason and date the subject is discontinued from double-blind treatment will be documented in the eCRF.

Subjects who fulfil the criteria for rescue treatment will be scheduled for a WLL as described in *Section 9.4*. Subjects receiving a WLL should continue Double-blind treatment and attend the remaining visits in the Double-blind treatment period and then continue into the Follow-up period.

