- ANCOVA based on the per protocol set (PPS).

Mean profiles for 6MWD and SGRQ over time will be provided.

Time to WLL during 24-weeks treatment

Kaplan-Meier plots will be used to assess time to WLL (time from randomisation to documentation of fulfilment of criterion for requiring WLL) and treatment comparisons corresponding to those made for primary endpoint, will be analysed by a logrank test adjusting for the randomisation strata (WLL). Subjects who fulfil the criteria for rescue treatment (i.e., worsening of aPAP based on symptoms, reduced exercise capacity and/or findings of hypoxemia or desaturation according to the Investigator's judgement), will be counted as if WLL was conducted at the date of fulfilment of rescue treatment criteria. In this analysis, subjects withdrawing from the trial will be handled as censored at time of discontinuation, and subjects who reach week 24 and have not needed WLL will be censored at time point for Visit at week 24. Survival estimates for time to WLL will be tabulated for subjects in each group who require WLL, by relevant time points, along with 95% Cis.

Sensitivity analyses for time to WLL will be carried out as follows:

- Any subject withdrawing from trial before week 24 and before fulfilling criteria for WLL will be handled as having WLL the day after discontinuation date. This is done to

evaluate the impact of missing data and censoring due to withdrawals. The same analyses as planned above will be conducted in order to evaluate the robustness of results with regards to the handling of censoring.

- A Cox regression will be applied where the hazard ratio and its 95% confidence interval will be estimated, while including adjustment for treatment, Japan vs other countries and WLL (stratification). The analysis will be done using the same approach for handling censoring as done in the main analysis.

Further Secondary Efficacy Analyses

The further secondary efficacy endpoints will be statistically analysed, although the analyses will be considered supportive rather than confirmatory, and will therefore not be part of the testing procedures implemented for primary and key secondary efficacy endpoints to control for multiplicity.

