Figure	14.2.2.36	Forest Plot for analyses of change from baseline in SGRQ total score, Molgramostim Int. vs Placebo by subgroups		X					
Table	14.2.2.37	Summary of number of subjects in need of WLL during 24-weeks of treatment		X	X				
Table	14.2.2.38	Life table summary of time from randomization to need of WLL		X					
Figure	14.2.2.39	Kaplan – Meier plot for time to need of WLL during 24-weeks of treatment		X					
Table	14.2.2.40	Analysis of difference between treatment groups (logrank test) in time to WLL during 24 weeks of treatment		X					
Table	14.2.2.41	Sensitivity analysis of difference between treatment groups (Cox regression) in time to WLL during 24 weeks of treatment		X					
Table	14.2.2.42	Sensitivity analysis of difference between treatment groups (logrank test) in time to WLL during 24 weeks of treatment – alternative censoring		X					
Table	14.2.2.43	Sensitivity analysis of difference between treatment groups (logrank test) in time to WLL during 24 weeks of treatment			X				
Table	14.2.2.44	Summary of number of subjects in need of WLL during 24-weeks of treatment by Age Group		X					
Table	14.2.2.45	Summary of number of subjects in need of WLL during 24-weeks of treatment by Sex		X					
Table	14.2.2.46	Summary of number of subjects in need of WLL during 24-weeks of treatment by aPAP severity		X					
Table	14.2.2.47	Summary of number of subjects in need of WLL during 24-weeks of treatment by aPAP diagnosis		X					
Table	14.2.2.48	Summary of number of subjects in need of WLL during 24-weeks of treatment by strata and by visit		X					
Figure	14.2.2.49	Kaplan – Meier plot for time to need of WLL during 24-weeks of treatment by strata		X					
Table	14.2.2.50	Summary of number of subjects in need of WLL during 24-weeks of treatment by region		X					
Figure	14.2.2.51	Kaplan – Meier plot for time to need of WLL during 24-weeks of treatment by region		X					
Figure	14.2.2.52	Forest Plot for analyses of time to WLL , Molgramostim OD vs Placebo by subgroups		X					
Figure	14.2.2.53	Forest Plot for analyses of time to WLL, Molgramostim Int. vs Placebo by subgroups		X					
Table	14.2.2.54	Overview of statistical hypothesis testing for primary and key secondary efficacy endpoints according to testing procedure		X					
Further Secondary Efficacy Endpoints									
Table	14.2.3.1	Summary of VC (% predicted) and change from baseline in VC (% predicted) by visit during 24 weeks treatment		X					

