The observed event rate of WLL was low, only 4 events among 78 randomized subjects either having WLL and then discontinuing, or subjects still remaining in trial. For the calculations it was anticipated the sample size would be calculated assuming 5% of subjects on active treatment vs 20% on placebo would have an event. Given these assumed event rates, and assuming an exponential distribution of survival times, at least 47 subjects would be needed to detect a difference between treatment groups using a log-rank test, with 80% power, and 63 subjects with 90% power, if these event rates are true. Given the low event rate, even though probably slightly underestimated in observed subjects, these calculated sample sizes are likely too optimistic.

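### The per-protocol log-rank test of time to WLL keeps only subjects who completed Visit 8, so it drops WLL events followed by withdrawal and selects on the future; this affects a supportive analysis only (minor)

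*SAP*

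**What the plan says.** SAP section 4 limits DB-PPS to "All randomised subjects who have completed Visit 8 and are deemed to have no important protocol deviations". Protocol 12.1.1 has the same rule. Neither text makes an exception for a subject who already had the event of interest.

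SAP section 4 then extends the set to the key secondary endpoints: "Although analyses of primary and key efficacy endpoints will be performed on both the DB-FAS and the DB-PPS". The same sentence adds that "the DB-FAS will be considered the primary analysis population". Time to WLL is a key secondary endpoint (SAP 2.2). Appendix 1 carries this through with Table 14.2.2.43, "Sensitivity analysis of difference between treatment groups (logrank test) in time to WLL during 24 weeks of treatment", marked under DB-PPS, and Table 14.2.2.37, the number of subjects in need of WLL, marked under both DB-FAS and DB-PPS.

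The main analysis in SAP 5.3.7 works differently. The event is dated when the WLL criterion is met, whatever follows, and "subjects withdrawing from the trial will be handled as censored at time of discontinuation". It does not need Visit 8. The time-to-WLL sensitivity analyses named in SAP 5.3.7 are alternative censoring and a Cox model. The per-protocol version comes only from section 4 and the table list.

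**The concern.** Requiring Visit 8 suits an endpoint measured at Week 24, because without that visit there is no value to analyse. Time to WLL needs no Week 24 measurement, since censoring deals with incomplete follow-up. Here the requirement selects subjects on something that happens after the event or censoring time.

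Take a subject who meets the WLL criterion at Week 10 and withdraws at Week 14 with no important deviation. In DB-FAS this is an event at Week 10. In DB-PPS the subject does not exist. A subject who withdraws event-free at Week 14 contributes 14 weeks at risk in DB-FAS and nothing in DB-PPS.

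At stake is the use of the per-protocol analysis as a check. It is meant to show whether the result depends on important protocol deviations. As defined, it can differ from the main result because of withdrawal alone. With few events expected, one or two lost events can change how the table reads.

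**Working it through.** **Tracing the rule.** The plan states no figure on this point, so there is none to reproduce. Side by side, with no important deviation in any row:

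| Subject | DB-FAS log-rank | DB-PPS log-rank |
|---|---|---|
| WLL criterion met, attends Visit 8 | event | event |
| WLL criterion met, withdraws before Visit 8 | event | absent |
| No WLL, withdraws before Visit 8 | censored at withdrawal | absent |
| Stops trial drug, attends Visit 8 | kept | kept |

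Only the second and third rows differ. The general rule in Protocol 8.4.1 points the other way: "If a subject is withdrawn from the trial, all data collected until the time of withdrawal will be used in the analyses". So does the blinded re-estimation (SAP 3.2), which counted subjects who met the WLL criterion before Week 24 and excluded only withdrawals without WLL.

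**Inputs for sizing.** From the SAP: planning rates of 20% (placebo) and 5% (active) at 24 weeks (3.2), 45 per arm (3.2), two-sided tests (5.3.1) and 0.05 (5.4). Assumed, because the documents do not give them: f, the share of WLL subjects who leave before Visit 8 (0 to 0.5), and w, the share of event-free subjects who leave (0 or 0.10). The full-set hazard ratio is ln(0.95)/ln(0.80) = 0.230.

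**Event rates and hazard ratio, f and w equal across arms.** For a true rate p, the DB-PPS rate is p(1−f) / [p(1−f) + (1−p)(1−w)]. With w = 0.10:

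| f | Placebo | Active | Hazard ratio |
|---|---|---|---|
| 0 | 0.200/0.920 = 21.7% | 0.050/0.905 = 5.5% | 0.232 |
| 0.3 | 0.140/0.860 = 16.3% | 0.035/0.890 = 3.9% | 0.226 |
| 0.5 | 0.100/0.820 = 12.2% | 0.025/0.880 = 2.8% | 0.222 |

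The hazard ratio is ln(1 − active)/ln(1 − placebo), from unrounded rates. The arm rates move, upward when f < w and downward when f > w. When f = w the formula returns p exactly. The contrast between arms hardly moves.

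**Events and power, f equal across arms, w = 0.** Expected events are 45 × 0.20 × (1−f) and 45 × 0.05 × (1−f). Schoenfeld power is Φ(|ln HR| × √(d/4) − 1.96), with d the total events and HR taken from the rate formula. The simulation used exponential times, 24 weeks of follow-up, an unstratified two-sided log-rank test and 4,000 runs.

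| f | Events, placebo / active | HR | Schoenfeld | Simulated |
|---|---|---|---|---|
| 0 | 9.0 / 2.25 | 0.230 | 69% | 61% |
| 0.10 | 8.1 / 2.0 | 0.228 | 65% | 57% |
| 0.25 | 6.75 / 1.69 | 0.225 | 58% | 50% |
| 0.50 | 4.5 / 1.13 | 0.221 | 43% | 35% |

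A second simulation with w = 0.10 (3,000 runs per f) gave DB-FAS power of about 0.57 and DB-PPS power of 0.57, 0.44 and 0.31 at f = 0, 0.3 and 0.5.

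**f different by arm, w = 0, simulated.**
- 50% leaving in placebo only: apparent rates of 11% vs 5%, power 16%.
- 50% leaving in active only: power 79%.
- True rates of 20% in both arms, 50% leaving in one arm only: the test rejects in 19 to 20% of runs against a nominal 5%.

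These are deliberately extreme settings. They show that bias can go either way, not how large it will be.

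**Scale against the events seen.** The blinded review found 4 events among 78 subjects (5.1%; SAP Appendix 2, 1.3), against a planned pooled rate of (5% + 5% + 20%)/3 = 10%. If one of four such subjects left after WLL, the count would be 3/77 (3.9%). If two left, it would be 2/76 (2.6%).

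**The case against.** The strongest reply is that no inference depends on this analysis. DB-FAS is primary, its log-rank test keeps every such event, and SAP 5.4 treats sensitivity analyses as supportive, with no multiplicity adjustment. Withdrawal is also tested on DB-FAS by counting event-free withdrawals as events (SAP 5.3.7, Table 14.2.2.42). All of this stands and limits the severity.

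Second, the plan works to keep f small. Protocol 8.4.2 says "Subjects receiving a WLL should continue Double-blind treatment and attend the remaining visits in the Double-blind treatment period" and asks subjects who stop treatment to attend Week 24 as a minimum. Protocol 8.4.1 asks for Week 24 assessments even after trial withdrawal. This also stands: f = 0.3 or 0.5 is hypothetical, and at f = 0.10 simulated power falls only from 61% to 57%. One gap remains. SAP 5.3.1 moves early-withdrawal assessments entered on the Week 24 page to an earlier visit. That suggests such subjects have not completed Visit 8, but the SAP does not say so.

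Third, a per-protocol set of completers without important deviations is a recognisable choice. That is fair for Week 24 change scores. It does not justify removing an event that has already occurred from a time-to-event analysis.

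Two stronger readings are tempting. A reader might infer that the per-protocol test is inherently biased against active treatment because placebo has more events to lose. With equal f the hazard ratio stays between 0.22 and 0.23; bias needs unequal f, and no text gives f by arm. A reader might also infer from Appendix 2 ("only 4 events among 78 randomized subjects either having WLL and then discontinuing, or subjects still remaining in trial") that subjects were seen to leave after WLL. That wording says who was counted. It does not report that anyone took this path.

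**Conclusion.** The point holds for a supportive analysis and is minor. The definition of DB-PPS, applied through Tables 14.2.2.37 and 14.2.2.43, removes WLL events followed by withdrawal and removes event-free withdrawals that should be censored. This follows from the text and needs no assumption. The confirmatory DB-FAS test and the multiple-testing procedure are untouched.

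The size is unknown because f is not in the documents. With equal f, at the SAP's planning rates and 45 per arm, the cost is events and power: roughly 0.57 to 0.61 at f = 0, 0.57 at f = 0.1 (w = 0), 0.44 at f = 0.3 (w = 0.10) and 0.31 to 0.35 at f = 0.5. Where a range is given, the lower figure has w = 0.10 and the higher has w = 0. All rest on exponential times and an unstratified test, whereas the planned test is stratified. With unequal f the comparison can be biased in either direction. The documents do not support a claim about which direction, or that it will occur.

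**What to change.** Before unblinding, add one sentence to SAP section 4 or 5.3.7. For time to WLL, per-protocol membership depends only on the absence of important protocol deviations; events are counted up to withdrawal, and event-free withdrawals are censored at withdrawal, as in DB-FAS. Keep the Visit 8 condition for the Week 24 endpoints, and state whether assessments reallocated under SAP 5.3.1 count as a completed Visit 8.

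Because the condition also stands in Protocol 12.1.1, list the departure in SAP 5.1.

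Under the planning assumptions, and before any exclusion for deviations, this restores the expected 9.0 and 2.25 events per 45 subjects and simulated power of about 61% (w = 0), the same as DB-FAS.

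The cost is the added text, a second per-protocol flag for Tables 14.2.2.37 and 14.2.2.43, and a per-protocol set for this endpoint that differs slightly from the one used elsewhere. No new data are needed.

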5 STATISTICAL AND ANALYTICAL PLANS

The planned tables, figures and listings are presented in Appendix 1.

5.1 Changes in the Planned Analyses

This SAP is based on protocol versions and amendments described in section 1. Compared to these, the following changes have been implemented in the SAP:

- All model-based analyses will include adjustment for a dichotomous categorization of country as Japan vs other countries.
- A number of additional subgroup analyses were added, as described in section 5.8.
- An additional sensitivity analysis for the primary endpoint was added for handling of subjects who had a WLL (section 5.3.6)
- Number of WLLs over time, was included as a further secondary endpoint in the double-blind period, as described in section 5.3.7.

5.2 Blind Review

The trial will be unblinded and the primary analysis will be conducted after all subjects have completed the 24-week Double-blind period. Data will be reviewed on an ongoing basis before the database is locked and unblinded. Clarifications of specific data decisions, having an impact on the planned analyses, which are identified in connection to the blind review, after finalization of the SAP, will be included in a separate “pre-analysis review” document, which will be signed before unblinding. Final classification of subjects according to study populations will be also documented and included in the pre-analysis-review document.

In this trial, analyses related to the double-blind (DB) treatment period will be reported after last subject has completed the treatment period, thus a partial DB data base lock will be held and all data up to that point will be cleaned and locked before unblinding. Further data review and cleaning, related to the open label follow-up period, will be done and any new decisions will be documented in a separate pre-analysis review document before a final complete FU data base lock. Locked data for the double-blind period cannot be changed after the partial data base lock, except for any ongoing safety evaluations that have not yet been resolved at the time point of the partial DB data base lock.

5.3 Hypotheses and Statistical Methods

5.3.1 General

For all efficacy analyses, primary and secondary, where statistical tests are conducted (see separate sections below) the null hypothesis is that there is no treatment difference, which

will be tested against the alternative hypothesis, that there is a treatment difference. All tests will be two-sided.

In general, all summary statistics will be presented for all treatment groups.

In this trial, for subjects withdrawing from treatment early, attempts will be made to continue follow-up and collect the planned data, as described in protocol. If a subject is withdrawn from the trial early, the investigator should attempt to complete all required trial assessments (such as those at Week 24 if withdrawn during the Double-blind treatment period). Assessments for subjects withdrawing from trial early, and where any measurements related to endpoints to be statistically analysed are collected on the Week 24 Visit in the eCRF, (i.e. if intermittent visits are missing), then these assessments will be reallocated to the visits closest in time to the time point of withdrawal. This is done in order to avoid an unintended partial LOCF approach to analysis of data.

For statistical analyses of the primary and key secondary efficacy endpoints, the type-1 error rate will be controlled, as described in section 5.4. In addition a number of sensitivity analyses will be conducted, as described in the following sections. An overview of the planned statistical analyses and how inflation of alpha, due to multiple testing, will be prevented can be seen in figure 2.

Results applicable to the follow-up period will be summarised both according to randomised treatment arms under the double-blind treatment period and in total.

5.3.2 Definitions

Baseline	Baseline measurements refers to the last non-missing assessment made before randomisation. If a measurement is intended to be collected at the baseline visit, but is missing, then a corresponding measurement taken at the screening visit may be used to replace the missing assessment at the baseline visit.
Relative day	The relative day of an event is derived as follows: $\text{Relative day} = (\text{Start date}) - (\text{Date of first administration of IMP}) + 1.$ For days before the start date, calculate as $\text{Relative day} = (\text{Start date}) - (\text{Date of first administration of IMP})$. In this way, there will be no day=0. So, Day 1 is the same day as the day of first administration of IMP, and Day -1 is the day before.
(A-a)DO ₂	Alveolar-arterial oxygen difference is a measure of the difference between the alveolar concentration (A) of oxygen and the arterial (a) concentration of oxygen
DLCO	Uptake of carbon monoxide from a single inspiration in standard time.
FEV ₁	The volume of air that can forcibly be blown out in one second, after full inspiration.
FVC	The maximum amount of air a person can expel from the lungs after a maximal inhalation and during a forceful expiration.
SpO ₂	Indirect measurement of oxygen saturation using a finger probe, ear sensor or similar device.
6MWT	Test used to measure the distance that a subject can walk quickly on a flat hard surface in a period of 6 minutes (at an individually predetermined oxygen supplementation).
VC	The maximum amount of air a person can slowly expel from the lungs after a maximum slow inhalation.
% predicted	Calculation of % predicted of spirometry parameters collected during the double-blind period will be made centrally for statistical analysis using the same equation for all sites.
Region	For summaries and figures split by region 'Europe' will include: Denmark, France, Germany, Greece, Italy, Netherlands, Portugal, Russia, Slovakia, Spain, Switzerland and United Kingdom. 'Other' will include: Australia, Israel, South Korea and Turkey while Japan and the United States will be defined as their own regions.

